8.2 Investigator pooling for secondary analyses

Investigator pooling will be done for secondary analyses where model contain investigator effect.

Pooling will be based on:

- 1) sites with less than 16 subject within each state will be pooled together geographically but can't over 40 subjects;
- 2) if a state with more than 40 subjects, sites within the state can be pooled geographically or sites will be pooled with neighbor state(s) geographically;
- 3) if a state with less 16 total subjects, then the sites will be pooled with other state (but can't be exceeded 40 subjects) geographically.

Pooling will be done prior to database lock and will be documented in the final BDR report.

8.3 Subject disposition

The number of patients screened, run-in, randomized, and included in each analysis population, along with study completion status, will be summarized by treatment group as well as overall. In addition, the number of patients who discontinue from the study and from IMP will be summarized by discontinuation reason. And the number of patients who discontinue from the run-in period will be summarized by discontinuation reason too.

The denominator used for the calculation of percentages will be the number of subjects randomized.

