3.3 Study treatments and assessments

During the Run-in period, all subjects will receive FlexPen NovoLog[®] from Novo-Nordisk (US listed drug) 100 U/mL until randomization. In addition, all patients will be shifted from their current basal insulin to Lantus[®] SoloSTAR[®] at the start of the run-in period, and will continue this for the complete study duration. The doses of NovoLog[®] and Lantus[®] will be titrated (if required) during the run-in period to ensure diabetes control.

During the Treatment period, all patients will receive one of the following treatments:

- MYL-1601D or FlexPen NovoLog[®] to be taken at meal time. Both investigational products will be provided in a pre-filled disposable pen with a 3-mL cartridge. During the treatment period, dose titration will be kept to a minimum.
- Once daily Lantus[®] SoloSTAR[®] (insulin glargine injection, 100 U/mL), manufactured by Sanofi-Aventis.

A detailed description of procedures and assessments to be conducted during this study is summarized in the Scheduled of Study Assessments in Table 1 below.

Table 1: Schedule of Study Assessments

Study Periods	Screening	Run-in Period				Randomized Comparative Treatment Period										Follow-up
Study Visits ¹	V1	V2	V3	V4	V5	V6	V7	V8	V9	V10	V11	V12	V13	V14	V15 (EOT) ¹⁰	V16 (FU)
Study Week	-7 to -4	-4	-3	-2	-1	0	1	2	4	8	12	16	20	22	24	28
Study Days	-49 to -28	-28±3	-21±3	-14±3	-7±3	0±3	7±3	14±3	28±3	56±7	84±7	112±7	140±7	154±7	168±7	196±7
Informed Consent	x															
Inclusion/Exclusion Criteria Review	x					x										
History of previous insulin usage	x															
Dilated Ophthalmoscopy / retinal photography (if not done the last 6 months)	x															
Standard-of-care specifics ²	x	x	x	x	x	x	x	x	x	x	x	x	x	x	x	
Age, Gender, Height, Race	x															

Study Periods	Screening	Run-in Period				Randomized Comparative Treatment Period										Follow-up
		V1	V2	V3	V4	V5	V6	V7	V8	V9	V10	V11	V12	V13	V14	
Study Week	-7 to -4	-4	-3	-2	-1	0	1	2	4	8	12	16	20	22	24	28
Study Days	-49 to -28	-28±3	-21±3	-14±3	-7±3	0±3	7±3	14±3	28±3	56±7	84±7	112±7	140±7	154±7	168±7	196±7
Body Weight and BMI ¹¹	x	x		x		x		x	x	x	x	x	x		x	
Pregnancy Test ³	x	x				x			x	x	x	x	x		x	
Medical History and concomitant illness	x															
Concomitant Medications	x	x	x	x	x	x	x	x	x	x	x	x	x	x	x	x
Vitals signs measurement (sitting)	x	x		x		x		x	x	x	x	x	x		x	
Physical examination	x					x									x	
12-lead ECG (supine)	x														x	

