6.2 ITT analysis set

The ITT analysis set includes all randomized subjects without being in the site with GCP violation (including subjects who receive incorrect treatment, do not complete the study or do not comply with the protocol or used prohibited medication, randomized but do not take any study drug). The subjects who are in the site with GCP violation will be excluded from ITT analysis set.

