6.5 Run-in analysis set

Run-in analysis set includes all subjects who enrolled into run-in period.

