8.6 Extent of exposure

8.6.1 Treatment duration

Duration of study drug (in days) will be calculated as: last dose date – first dose date + 1 day, regardless of study drug interruption.

Study drug exposure will be summarised by treatment group as well as overall on the ITT analysis set using descriptive statistics for run-in period and treatment period.

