8.8 Safety analyses

Safety data from the run-in period will be summarized and listed on run-in analysis set.

Descriptive statistics will be provided for the following safety data. No inferential analysis of this safety data is planned. Any Vital signs, ECG, and Laboratory abnormalities of potential clinical concern will be described.

For the continuous safety measures, both actual and change values will be summarized at baseline and scheduled visit. Similar MMRM model as efficacy analysis will be conducted for hypoglycemia rate. For antibody continuous variables, the MMRM model will include the fixed, categorical effect of treatment group assignment, visit, treatment group-by-visit interaction and the other fixed effect terms investigator and baseline value as covariates. Contrasts of LS mean at each scheduled visit will be used to evaluate all pairwise treatment comparisons, and 95% confidence intervals for treatment differences in LS means will be computed for each visit. For categorical data analyses, Fisher's exact test or Chi-squared test will be used.

The following analyses will also be performed.

- Incidence of ADA response, incidence of positive cross-reactive ADA, and incidence of positive NABs
- Analysis of potential impact of TEAR status on efficacy and safety parameters such as HbA1c, FPG, insulin dose hypoglycemic rate, and incidence of any injection site allergic reactions and hypersensitivity
- Change in hypoglycemia rate (30 day adjusted) from baseline and incidence of hypoglycemic events at scheduled visits
- Incidence of TEAEs and SAEs
- Incidence of local allergic reactions, systemic allergic reactions and other adverse events
- Incidence of device-related safety assessment

To explore the potential ADA impact on subject's glucose control, the following analyses will be performed:

- The incidence of subjects with each of the three following criteria will be summarized descriptively (for categorical measures) by treatment:
 - 1) Meet TEAR criteria
 - 2) Increases in HbA1c of over 0.2% from baseline
 - 3) Increase in total dose from baseline
- Scatter plots of maximum tear values with HbA1c FPG and total daily insulin dose by treatment.

All the above analyses will be performed on the safety set.

In addition, graphical visualization of relationship between adverse events and treatment duration will be provided.

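### SAP 8.3 uses the number randomized as denominator even for run-in discontinuations, and SAP 8.6.1 reports run-in exposure only on ITT; a descriptive-reporting fix is needed

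*SAP*

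**What the plan says.** SAP Section 8.3 tabulates how many patients were screened, entered the run-in, were randomized and fell into each analysis population, by treatment group and overall. It adds that "the number of patients who discontinue from the run-in period will be summarized by discontinuation reason too". It closes with a single denominator rule: "The denominator used for the calculation of percentages will be the number of subjects randomized". It makes no exception for items that arise before randomization.

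SAP Section 8.6.1 summarizes study drug exposure by treatment group and overall "on the ITT analysis set using descriptive statistics for run-in period and treatment period". Section 6.2 defines that set: "The ITT analysis set includes all randomized subjects without being in the site with GCP violation".

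The SAP also has a set that fits the run-in. Section 6.5 states: "Run-in analysis set includes all subjects who enrolled into run-in period". Section 8.8 uses it: "Safety data from the run-in period will be summarized and listed on run-in analysis set". Section 8.8.1 repeats this for run-in adverse events. (Run-in device summaries in Section 8.8.2 are placed on the safety set instead.) Neither 8.3 nor 8.6.1 refers to the run-in analysis set.

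Run-in subjects are exposed to study-supplied drug. Section 3.3 says: "During the Run-in period, all subjects will receive FlexPen NovoLog[®] from Novo-Nordisk (US listed drug) 100 U/mL until randomization". They are also moved to Lantus.

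**The concern.** A subject who discontinues in the run-in cannot be among the randomized. Under the 8.3 rule the numerator is therefore not part of the denominator, and the result is a ratio of failures to successes, not a proportion of those at risk.

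For exposure, every ITT subject reached the randomization visit. A run-in exposure summary on ITT leaves out all those who stopped earlier, who are also the ones with the shortest exposure.

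What is at stake is the description of the run-in. All subjects are put on the same NovoLog and Lantus regimen there, and Protocol Section 2.2 relies on it to make drug exposure comparable before randomization. How many left, why, and after how much drug tells a reader to whom the randomized comparison applies.

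**Working it through.** **Percentages.** The plan states no run-in attrition figure, so there is none to reproduce. The inputs are:

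- R, the number randomized: 500 planned (Protocol Section 4.1).
- f, the true run-in failure rate: not in the documents; assumed to lie between 5% and 30%.
- E, the number entering the run-in: E = R/(1-f).
- D, the run-in failures: D = E - R.

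The percentage under SAP 8.3 is D/R = f/(1-f). On the run-in analysis set it is D/E = f. The ratio of the two is 1/(1-f), which exceeds 1 for any f above zero.

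| Assumed f | E = 500/(1-f) | D = E - 500 | SAP 8.3: D/500 | Run-in set: D/E |
|---|---|---|---|---|
| 5% | 526.3 | 26.3 | 5.3% | 5.0% |
| 10% | 555.6 | 55.6 | 11.1% | 10.0% |
| 20% | 625.0 | 125.0 | 25.0% | 20.0% |
| 30% | 714.3 | 214.3 | 42.9% | 30.0% |

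In whole subjects, 100 failures with 500 randomized would print as 100/500 = 20.0%, against 100/600 = 16.7% of those who entered the run-in. At 25 failures the pair is 5.0% and 25/525 = 4.8%; at 150 it is 30.0% and 150/650 = 23.1%.

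**What can be recovered.** Section 8.3 reports both the number entering the run-in and the number discontinuing from it, by reason. A reader can divide one by the other, so no attrition information is lost.

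**Exposure.** Here no arithmetic is needed; the sets decide it.

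- Run-in analysis set (6.5): everyone enrolled into the run-in, with no site exclusion.
- ITT (6.2): randomized subjects, less the site with GCP violation.
- Present in the first and absent from the second: every run-in failure and every run-in subject at the excluded site.

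Section 8.6.1 derives duration as last dose date minus first dose date plus one day and summarizes it on ITT only. Section 7.1 derives extent of exposure from randomized medication only. By default, Section 8.1 bases data listings on randomized subjects. No section provides run-in exposure for those who left before randomization, so, unlike the percentage, it cannot be rebuilt from the planned output.

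**The case against.** The strongest reply on 8.3 is that the section promises numbers of patients for the pre-randomization rows and does not say that percentages will be printed there. Section 8.1 speaks of percentages out of the appropriate population, with the denominator shown when needed. Section 1 places the table templates in a separate document, which may set row-level denominators. This stands in part: a percentage on these rows is an inference. But 8.3 has a specific rule without an exception, so a programmer who follows it and prints a percentage gets the wrong one. For the same reason, a reader might infer that the screened and run-in rows will show more than 100%. The SAP does not say that those rows carry percentages.

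On 8.6.1, the by-arm ITT summary has a sound purpose. Protocol Section 2.2 wants comparable exposure before randomization, and a between-arm view needs subjects who have an arm. That stands. It argues for keeping the ITT summary, but not for having no summary of the rest.

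A reader might also infer that run-in failures contribute adverse events but no exposure, so that event rates are distorted. The documents do not support this. Adverse events are summarized as subject counts and percentages (Section 8.8.1), and the hypoglycemia rate uses each patient's days between visits (Section 8.8.3). Neither uses the 8.6.1 exposure summary.

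A further temptation is to ask that treatment-period exposure move from ITT to the safety set. Both sets exclude the same site. They differ only for subjects never dosed and, in grouping, for those given the wrong treatment. That is a preference, and the documents offer no figure to show that it matters.

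Finally, the failure rate is assumed. Subjects enter on a stable basal-bolus regimen (Protocol Section 4.2.1), and Protocol Section 6.3.1 sets no glycemic threshold for leaving the run-in. Attrition may be low, and at 5% the discrepancy is only 0.3 percentage points.

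**Conclusion.** The point holds as a minor defect in descriptive reporting, in two parts.

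First, the 8.3 denominator rule gives a wrong percentage wherever one is printed for run-in discontinuations. It is always too high, by the factor 1/(1-f): 1.05 at 5% failure, 1.43 at 30%. The size depends on a failure rate that the documents do not give; the direction does not. It would be wrong to conclude that run-in failures go uncounted, since their numbers and reasons are reported.

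Second, the 8.6.1 run-in exposure summary omits everyone who left before randomization and is tilted toward full run-in length. This part rests on the set definitions alone and needs no assumption.

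The primary TEAR analysis, its error rate and its power are untouched.

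**What to change.** In SAP 8.3, state the denominator by stage:

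- Screening rows: counts only, or the number screened.
- Run-in discontinuations: the run-in analysis set, in an overall column only, because no arm exists yet.
- Post-randomization rows: the number randomized, as now.

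In SAP 8.6.1, keep the by-arm ITT summary of run-in exposure and add an overall summary on the run-in analysis set. Leave treatment-period exposure as planned.

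The cost is about two sentences in the SAP, a denominator change in the disposition table and one added summary in the exposure table. The run-in analysis set is already defined, and no new data are needed.

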8.4 Protocol deviations

All protocol deviations identified will be summarized by treatment group and overall and by classification, i.e., major and minor.

Summaries will be conducted on all subjects that were randomized.

8.5 Demographics and baseline characteristics

No statistical testing will be performed for the comparison between treatment groups on demographics and baseline characteristics.

8.5.1 Demographics

Subject demographics will be summarized by randomized treatment group, as well as overall for all subjects in the ITT analysis population. Age, height, weight and BMI at baseline will be summarized using an 8-number summary (n, mean, standard deviation, median, 25th quartile, 75th quartile, minimum and maximum values). Qualitative variables such as gender, child-bearing potential status, ethnicity and race will be summarized using count and percentage.

A by-subject listing will be provided.

8.5.2 Baseline and disease characteristics

The categorical baseline characteristics such as duration of DM, time of basal dose, TEAR, HbA1c, FPG, insulin used prior to screening, baseline ECG and other baseline lab parameters will be summarized using frequency counts for the ITT analysis population.

A by-subject listing will be provided.

8.5.3 Medical history

A summary of medical history will be summarized by treatment group, as well as overall, by system organ class (SOC) and preferred term (PT) using latest version of Medical Dictionary for Regulatory Activities® (MedDRA) for the ITT analysis population.

A by-subject listing will be provided.

8.5.4 Concomitant medications

Medications used in this study will be coded by using the latest available version of the World Health Organization Drug Dictionary Enhanced (WHODDE).

Prior medications: are defined as medications taken within 28 days prior to screening and prior to dosing with study medication.

Concomitant medications: are defined as medications that were ongoing at the time of first dose of study medication or new medications that started after first dose of study medication and within 28 days following the date of the last dose of study medication.

Prior medications and concomitant medications will be summarized descriptively using frequency tables by anatomical therapeutic chemical (ATC) class and preferred name by treatment group, as well as overall on the ITT analysis population.

A by-subject listing will be provided.

Details for imputing missing or partial start and/or stop dates of medication are described in Section 7.2.3.

8.6 Extent of exposure

8.6.1 Treatment duration

Duration of study drug (in days) will be calculated as: last dose date – first dose date + 1 day, regardless of study drug interruption.

Study drug exposure will be summarised by treatment group as well as overall on the ITT analysis set using descriptive statistics for run-in period and treatment period.

8.6.2 Treatment compliance

Patient will be identified as study treatment non-compliant if the patient meets any following criteria:

- Missing total meal time insulin daily
- Missing basal insulin daily
- Took two times more basal insulin daily
- Took less or more than prescribed basal insulin dose units daily

Number and proportion of patients with non-compliance will be summarized along with individual categories of non-compliance for each category.

The non-compliance proportion is defined as total accumulative non-compliant days divided by duration of treatment exposure in days. Summary of non-compliance proportion will be performed by each non-compliance category for each treatment group. The treatment groups will be compared by using an ANOVA model which will include treatment and pooled-site. Treatment compliance will be summarized on the ITT analysis set.

8.7 Efficacy analyses

This section addresses separately the analyses to be conducted on the primary and secondary efficacy variables. The primary analysis population for efficacy analyses will be the ITT population, although some analyses may be repeated for other analysis sets as indicated.

8.7.1 Analysis methods

Definition of Primary Endpoints

The TEAR rate during 24-week treatment period is the primary endpoint for this study. TEAR is defined as either one of the following:

- 1) Subjects who are ADA negative at baseline and become positive at any timepoint post baseline.
- 2) Subjects who are ADA positive at baseline and demonstrate 4-fold increase in titer values at any timepoint post baseline visit.

Although differences in TEAR rate is the primary endpoint for the study from a statistical perspective, given that immunogenicity is not a standard endpoint in clinical trials, this difference, even if significant, will not be assessed in isolation but will be part of totality of evidence including changes in HbA1c, FBG, insulin dose, neutralizing antibodies and injection site reactions to ensure that changes in TEAR rate, if any, are clinically correlated and meaningful.

Statistical Methodology for Primary Endpoint

The 90% confidence interval of the treatment difference (MYL-1601D minus NovoLog®) in the TEAR rate will be established using the Wald confidence limit method with multiple imputation (Section 8.7.2.1). The MYL-1601D TEAR rate will be declared equivalent to that of NovoLog® during the 24-week treatment period if the 90% confidence interval of the treatment difference in TEAR rate is within the pre-specified margin as displayed in Table 2 of the study SAP, as suggested by Chow et al. (2002; 2003). For specific reference drug rate-based margin calculation, please refer to the SAS example code in Section 10 (Appendices – SAS Example Codes).

The primary analysis will be based on the ITT population. In addition, all post-discontinuation and rescue data will be included in the analysis.

8.7.1.1 Multiplicity

No adjustment will be made for multiple comparisons.

8.7.1.2 Treatment by center interaction analysis (multi-center study)

No analysis will be made to assess the treatment-by-center interaction.

8.7.2 Analysis of primary efficacy endpoint(s)

The primary objective of the study is to assess whether MYL-1601D is equivalent to NovoLog® in immunogenicity, as assessed by the rate of treatment emergent antibody response (TEAR) during 24 weeks of treatment. The primary efficacy endpoint is the TEAR rate at Week 24. TEAR is defined as either one of the following:

- 1) Subjects who are ADA negative at baseline and become positive at any timepoint post baseline
- 2) Subjects who are ADA positive at baseline and demonstrate 4-fold increase in titer values at any timepoint post baseline visit.

8.7.2.1 Primary efficacy analysis

The primary efficacy analysis will be a test of equivalence for the MYL-1601D and NovoLog® groups in the TEAR rate at Week 24. The null hypothesis is non-equivalence, expressed by

$$H_0: |p_M - p_N| \geq \delta, \delta > 0$$

where p_M and p_N are the (true) proportions of subjects with TEAR in the MYL-1601D and NovoLog[®] groups, respectively, and δ is the equivalence margin. The null will be rejected in favor of equivalence if the 90% confidence interval of the treatment difference is within the range $(-\delta, \delta)$. The confidence interval as defined by Chow and Shao (2002) is constructed as

$$CI_{2\alpha} = [\hat{p}_M - \hat{p}_N - t_\alpha \hat{\sigma}, \hat{p}_M - \hat{p}_N + t_\alpha \hat{\sigma}]$$

where \hat{p}_j is the estimate of the TEAR rate p_j in each treatment group, $j \in \{M, N\}$, $\hat{\sigma}$ is the sample estimate of the standard error of the mean, and t_α the 0.05 quantile of the t distribution with $(N - 2)$ degrees of freedom with N being the pooled number of subjects in the analysis. That is, H_0 will be rejected if neither $-\delta$ nor δ is contained within the 90% confidence interval.

To minimize any bias due to missing data, the primary efficacy analysis will use multiple imputation to fill in missing ADA values. Multiple imputation (MI) will be applied to two measured variables: ADA binary response (positive/negative) and ADA continuous titer values. Multiple imputation will be done for each variable separately, then the two sets of imputed datasets will be merged in order to generate the imputed TEAR status. For subjects who are ADA negative at baseline, post-baseline missing values will be imputed using the binary response values obtained from logistic regression MI. Missing post-baseline values for subjects who are ADA positive at baseline will be derived from the continuous MI model. The primary efficacy analysis is based on the Week 24 (Visit 15) value. Subjects who discontinue treatment prematurely will be classified based on whether ADA values were obtained for the visits after treatment discontinuation (retrieved dropouts) or not.

For continuous-valued ADA titer, missing values prior to the last observed visit will be filled in with MCMC imputation to make the dataset monotone. Missing values after discontinuation will be imputed by regression imputation of the monotone missing dataset. If there are at least 6 retrieved dropouts in each treatment arm, then a pattern mixture model estimated from the retrieved values will be used for regression imputation of missing values. Otherwise, the complete case missing values method will be used. Missing values for the binary response variable will be imputed using a logistic regression multiple imputation model. A monotone missingness pattern will be created by taking a random draw from the binomial distribution with the same probability as the observed responses from the same treatment group at the same visit.

Pattern mixture models will be fit separately for ADA binary response and for ADA titer. Binary response will be imputed using a logistic regression imputation model, while ADA titer will use a continuous-valued regression. Independent variables in the regression will include the values at all prior visits. Each imputation will be repeated 30 times with a seed of 40872021 for ADA binary response and a seed of 41671703 for ADA titer. Code for the multiple imputation analyses is presented in Appendix 10.1.

If baseline value is missing, the missing baseline value will be imputed with six imputations based on binomial distribution using probability of no missing baseline values from same treatment group.

After imputation, the dataset containing the imputed visitwise TEAR positive or negative status binary response and the dataset containing the imputed ADA titer values will be merged by subject, visit, and imputation number. The Week 24 values will then be used to assign the status of TEAR positive or negative, as follows:

If the subject was ADA negative at baseline, then this subject will be considered TEAR positive if any post-baseline observed or imputed value was ADA positive; otherwise, the subject will be considered TEAR negative. The imputed titer values will not be considered in subjects who are ADA negative at baseline.

If the subject was ADA positive at baseline, then the imputed titer values will be used. The subject will be considered TEAR positive if the ADA titer at any post-baseline visit was $\geq 4\times$ the baseline titer. If none of the post-baseline titer values reached 4 times the baseline titer, then the subject will be classified as TEAR negative.

For each imputation, the proportion of responders, along with standard errors, will be estimated for each treatment group, and the estimate and standard error of the risk difference will be computed. These values will be combined across imputations using PROC MIANALYZE. Subsequently, the 90% confidence interval for the risk difference will be computed using the Wald confidence limit method.

An equivalence margin will be established as a function of the TEAR rate among the Novolog subjects. Under the null hypothesis of equivalence (i.e., $H_0: p_M = p_N$), the margin can be obtained as a function of the TEAR rate in the Novolog group using the following expression (Chow S-C et al., 2003, p. 91).

$$\delta = (z_\alpha + z_\beta) \sqrt{\frac{2p_N(1 - p_N)}{n_N}}$$

Selected values for δ are provided in Table 2 of Section 5 above. If the margin falls within the 90% confidence interval for the risk difference, then equivalence of MYL1601-D and Novolog will be declared.

These steps can be executed using code similar to the following:

```
proc freq data=simdata ;
title "90% Wald confidence interval";
by _imputation_;
ods output riskdiffcol2=rdiff1;
table group*resp / riskdiff (CL=WALD column=2) alpha=0.1;
weight count;
run;

data rdiff1; set rdiff1;
keep _imputation_ row risk ase lowercl uppercl;
if row='Difference';
run;

proc mianalyze data=rdiff1;
modeleffects risk;
stderr ase;
ods output ParameterEstimates=mirisk1;
run;

ods listing;
data parms1;
set mirisk1;
lowercl = estimate - (1.645*stderr);
uppercl = estimate + (1.645*stderr) ;
run;
proc print data=parms1;
var estimate stderr lowercl uppercl;
run;
```

